11.3.2 Statistical Methods

The baseline value for clinical laboratory tests will be the last non-missing measurement on or before the day of the first dose of study drug. Values on Day 1 must also be before the time of first dose if time is available. The same baseline value will be used for changes at Treatment Period visits and changes at Post-Treatment Period visits.

Changes from baseline to each post-baseline visit, including applicable post-treatment visits, will be summarized. Each protocol-specified laboratory parameter will be summarized with the sample size, baseline mean; visit mean; and change from baseline mean, standard deviation, minimum, median, and maximum.

Individual changes in the laboratory parameters listed in Section 11.3.1 will be tabulated using shift tables. Laboratory data values will be categorized as low, normal, or high based on normal ranges of the laboratory used for each sample. Shift tables from baselineto minimum value and maximum value during the Treatment Period will be created. For each parameter, the shift tables will cross tabulate the frequency of subjects with baseline values below/within the normal range to maximum above the normal range and with baseline values within/above the normal range to minimum below the normal range.

The laboratory parameters listed in Table 11 will be assigned a toxicity grade of 1, 2, 3, or 4. The number and percentage of subjects with a maximum toxicity grade of 1, 2, 3 or 4 will be tabulated. To be counted, the post-baseline value must have a toxicity grade that is more extreme than the toxicity grade corresponding to the baseline value. For each laboratory parameter in Table 11, the summary will also include the number and percentage of subjects with a maximum of at least grade 3. A listing of all relevant laboratory parameters will be provided for each subject who had an increase to grade 2 or higher for any laboratory variable in Table 11.

Assessment of Hepatic Laboratory Values

The number and percentage of subjects with laboratory values meeting the following criteria during treatment will be summarized:

- Post-nadir (preceding value is lower than the subsequent value) ALT $> 5 \times \text{ULN}$ (regardless of grade change);
- Total bilirubin $\geq 2 \times \text{ULN}$ and $>$ baseline (i.e., a post-baseline value must be more extreme than the baseline value to be considered);
- Post-nadir ALT $> 3 \times \text{ULN}$ and total bilirubin $> 2 \times \text{ULN}$;
- Post-nadir ALT $> 3 \times \text{ULN}$ and total bilirubin $\leq 2 \times \text{ULN}$.

Four listings (one for each bullet above) of all liver function tests including ALT, AST, total, indirect and direct bilirubin, ratio of direct to total bilirubin, and alkaline phosphatase values will be provided for each subject who met the criterion defined above.

Hepatic Laboratory Abnormalities of Interest

Among the events assessed under "Assessment of Hepatic Laboratory Values," the following criteria are of interest:

- Confirmed post-nadir ALT $> 5 \times \text{ULN}$;
- Post-nadir ALT $> 3 \times \text{ULN}$ and a concurrent total bilirubin $> 2 \times \text{ULN}$ with a direct bilirubin:total bilirubin ratio > 0.4 .

To support the assessment of hepatic laboratory abnormalities of interest, the following potential events will be summarized:

- Confirmed post-nadir ALT $> 5 \times \text{ULN}$;
- Post-nadir ALT $> 3 \times \text{ULN}$ and total bilirubin $> 2 \times \text{ULN}$ and direct/total bilirubin ratio > 0.4 .

Two listings (one for each bullet) of all liver function tests including ALT, AST, total, indirect and direct bilirubin, ratio of direct to total bilirubin, and alkaline phosphatase values will be provided for each subject who met the criterion defined above.

For the **assessments of hepatic laboratory values and hepatic laboratory abnormalities of potential interest**, the maximum ratio relative to the ULN will be used to determine if subjects meet any of the criteria listed above. The ALT and total bilirubin values do not need to be concurrent in order to meet the defined criteria in statistical summaries. For ALT, the post-baseline value must represent an increase from the first nadir (including baseline) to be counted. First nadir is defined as the last value prior to the first increase. For total bilirubin, a subject will be counted if the post-baseline laboratory value meets the above criteria regardless of the baseline laboratory value (i.e., the post-baseline laboratory value does not need to be worse than the baseline laboratory value), except where noted above. A confirmed post-nadir increase in ALT is defined as two consecutive values of $ALT > 5 \times ULN$ after nadir, either both during treatment or at the final treatment measurement and the next consecutive post-treatment measurement. A single post-nadir ALT value of greater than $5 \times ULN$ followed by lost to follow-up (no additional ALT values) also will be considered (i.e., will not require confirmation). The ratio of direct to total bilirubin will be calculated using the same date/time sample corresponding to the total bilirubin elevation.

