SVR ₁₂	Sustained virologic response 12 weeks post dosing
TE	Treatment Experienced
TN	Treatment-naïve
TSQM	Treatment Satisfaction Questionnaire-Medicine
ULN	Upper limit of normal
VAS	Visual Analog Scale
V/F	Apparent Volume of distribution
WBC	White blood cells
WOCBP	Women of child bearing potential

Definition of Terms

Study Drug	glecaprevir/pibrentasvir
Study Day 1	First day of study drug dosing
Treatment Period	Day 1 through last dose of study drug
Post-Treatment Period	Day after the last dose of study drug through Post-Treatment Week 12 or Post-Treatment Discontinuation

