Appendix D. Study Activities – Post-Treatment (PT) Period

Activity	PT Wk 4	PT Wk 12	PT D/C ^a
Vital Signs and Weight	X	X	X
Hematology/Chemistry/Coagulation Panel	X	X ^b	X ^c
Pregnancy Test (urine) ^d	X (u)	X ^e	X (u) ^c
Concomitant Medication Assessment ^e	X	X ^e	X ^e
Child-Pugh Score (cirrhotic subjects only)		X	X
Adverse Event Assessment ^f	X ^f	X ^g	X ^g
HCV RNA Samples	X	X	X
HCV Resistance Sample	X	X	X
Patient Reported Outcomes Instruments (PROs) ^h		X	X
Flow cytometry sample ^h	X	X	X
HIV RNA ⁱ	X	X	X
HCC Screening: Liver Ultrasound ^j		X	X

Wk = Week; PT D/C = Post-Treatment Discontinuation

- Subjects who prematurely discontinue from the Post-Treatment Period should return to the site to complete the PT D/C Visit procedures.
- Chemistry/Coagulation panel will only be collected at PT Wk 12 for subjects in Arm B (compensated cirrhosis).
- Hematology/Chemistry/Coagulation Panel and Pregnancy Test are not required at PT Wk 12, but only at PT D/C if subject discontinues prior to PT Wk 4.
- Women of childbearing potential do not require pregnancy testing beyond PTW4. Pregnancy testing will be performed at PT D/C visit only if the subject discontinues prior to PTW4. Pregnancy testing in PT Period is not required for females of non-childbearing potential as defined in Section 5.2.4.
- Only medications taken for SAEs and treatment of HCV will be collected after 30 days post-dosing.
- Nonserious AEs and all SAEs will be collected until 30 days post dosing. All spontaneously reported SAEs will be collected thereafter. See specific information regarding adverse event collection in Section 6.1.4.

- g. Only SAEs will be collected thereafter as described in Section [6.1.4](#).
- h. PROs should be administered before any study procedures in the order listed in Section [5.3.1.1](#).
- i. For HCV/HIV co-infected subjects.
- j. HCC Screening Liver Ultrasound performed only subjects in Arm B as described in Section [5.3.1.1](#).

Note: Day 1 of the Post-Treatment Period will be defined as the day after the last dose of study drug.

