6.2 Definition of Analysis Windows

For efficacy analyses of HCV RNA, the time windows specified in [Table 1](#) and [Table 2](#) describe how efficacy data are assigned to protocol-specified time points during the Treatment and Post-Treatment Periods, respectively. All time points and corresponding time windows are defined based on the date/time of blood sample collection.

For safety laboratory data, PRO data, Child Pugh score and vital sign data, the time windows specified in [Table 1](#) and [Table 3](#) describe how data are assigned to protocol-specified time points.

If more than one assessment are included in a time window, the assessment closest (except in analyses of SVR) to the nominal time will be used. If there are two observations equally distant to the nominal time, the latest one will be used in analyses. For analyses of SVR (e.g., SVR₁₂), the last value in the window will be used.

If multiple measurements are made on the same day for a safety laboratory parameter or a vital sign parameter, the average of the values will be used to calculate descriptive statistics and in analyses of the mean change from baseline. For summaries of shifts from baseline and potentially clinically significant values, multiple values on the same day will not be averaged; all values will be considered for these analyses.

Table 1. Analysis Time Windows for HCV RNA and Resistance Endpoints, Safety Laboratory and Vital Sign Measurements, Child Pugh Scores and PRO Instruments (Treatment Period)

Scheduled Visit	Nominal Day (Study Day)	Time Window (Study Day Range)
Day 1/Baseline ^a	1	≤ 1 ^a
Week 4	28	2 to 42
Week 8	56	43 to 70
Week 12 ^b	84	71 to 98
Final Treatment Visit ^c	2 to ≤ 2 days after last dose of study drug	

a. Day of first dose of study drug.

b. For 12-week treatment duration only.

c. The last value within the window will be used to define the Final Treatment Visit value. The upper bound of this Final window is Study Drug End Day 2. Study Drug End Day 0 is defined as the day of the last dose of study drug.

Note: For all windows, data must be on or before Study Drug End Day 2. The result closest to the scheduled time point will be used. PRO instruments are collected at Day 1 and End of Treatment Visit, which can be at Week 8, or 12 depending on treatment assignment, or Premature Discontinuation Visit.

Table 2. Analysis Time Windows for HCV RNA and Resistance Endpoints (Post-Treatment Period)

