Scheduled Visit ^a	Nominal Day (Study Drug End Day)	Time Window (Study Drug End Day Range)
Post-Treatment Week 4	28	3 to 56
Post-Treatment Week 12	84	57 to 126
SVR ₄ ^b	28	3 to 56
SVR ₁₂ ^b	84	57 to 126

a. Post-Treatment Visits are applicable for subjects who received at least one dose of study drug.

b. For SVR windows, the last value in the window will be used.

Note: The result closest to the scheduled time point will be used, except for SVR₄ and SVR₁₂. For all windows, data must occur after Study Drug End Day 2. Study Drug End Day 0 is defined as the day of the last dose of study drug.

Table 3. Analysis Time Windows for Safety Laboratory and Vital Sign Measurements, Child Pugh Scores and PRO Instruments (Post-Treatment Period)

Scheduled Visit ^a	Nominal Day (Study Drug End Day)	Time Window (Study Drug End Day Range)
Post-Treatment Week 4	28	3 to 56
Post-Treatment Week 12	84	57 to 999
Final Post-Treatment Visit ^b	> 2 days after last dose of study drug	

a. Post-Treatment Visits are applicable for subjects who received at least one dose of study drug.

b. The last value within the Post-Treatment Period window will be used to define the Final Post-Treatment visit value. The lower bound of this Final window is Study Drug End Day 3. Study Drug End Day 0 is defined as the day of the last dose of study drug.

Note: The result closest to the scheduled time point will be used. For all windows, data must occur after Study Drug End Day 2. Vital signs are collected at every post-treatment visit; hematology, chemistry and coagulation panels are collected at PTW4 or PT D/C (if subject discontinued prior to PTW4). PRO instruments and Child Pugh Scores are collected at PTW12 (or PT D/C).

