11.2.1 Treatment-Emergent Adverse Events

Treatment-emergent AEs are defined as any AE with an onset date that is after the first dose of study drug and no more than 30 days after the last dose of study drug. Events where the onset date is the same as the study drug start date are assumed to be treatment-emergent. If an incomplete onset date was collected for an AE, the event will be assumed to be treatment-emergent, unless there is other evidence that confirms that the event was not treatment-emergent (e.g., the event end date was prior to the study drug start date).

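### The hepatic criteria are counted only during treatment, so a post-nadir ALT rise or ALT-plus-bilirubin combination first seen at the scheduled PT Week 4 draw is in no hepatic count or hepatic listing

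*SAP*

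**What the plan says.** SAP 11.3.2 defines four hepatic criteria: post-nadir ALT above 5 x ULN; total bilirubin at least 2 x ULN and above baseline; post-nadir ALT above 3 x ULN with bilirubin above 2 x ULN; and the same ALT with bilirubin at or below 2 x ULN. The period is fixed by the lead-in: "The number and percentage of subjects with laboratory values meeting the following criteria during treatment will be summarized". The two abnormalities of interest inherit it: "Among the events assessed under 'Assessment of Hepatic Laboratory Values,' the following criteria are of interest". Each criterion has a listing, restricted to subjects who meet it.

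The section does not define the end of treatment. The note to SAP Table 1 (section 6.2) says of Treatment Period data: "For all windows, data must be on or before Study Drug End Day 2". Protocol 1.3 defines the Treatment Period as "Day 1 through last dose of study drug". Either boundary falls before the PT Week 4 visit.

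A post-treatment ALT has one role in 11.3.2. It can be the second, confirming value when the final treatment measurement already exceeded 5 x ULN.

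For adverse events, SAP 11.2.1 uses a longer period, with onset "no more than 30 days after the last dose of study drug".

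Chemistry continues after treatment. Protocol Appendix D schedules it at PT Week 4 for all subjects, at PT Week 12 for Arm B only, and at post-treatment discontinuation if that comes before PT Week 4. The note to SAP Table 3 says that "hematology, chemistry and coagulation panels are collected at PTW4 or PT D/C" (it omits the Arm B PT Week 12 panel).

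**The concern.** Safety is part of the primary objective, and ALT increase is the only laboratory abnormality with its own management section (Protocol 6.1.7.1). The hepatic tables are the only output that combines ALT with bilirubin or measures ALT from its nadir.

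The nadir rule is the part most exposed. Arm A has two scheduled on-treatment post-baseline draws, Week 4 and end of treatment (EOT). If ALT is still falling at EOT, the first scheduled draw that could show a rise from nadir is PT Week 4, and that draw cannot open a case. Similarly, the SAP lets ALT and bilirubin qualify on different dates, yet an ALT rise at EOT followed by a bilirubin rise at PT Week 4 does not count as a combination.

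The adverse event tables do not reliably fill the gap. Under Protocol 6.1.1.1 a laboratory abnormality is an adverse event only if it leads to discontinuation, needs medical intervention, or is judged to be one by the investigator.

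**Working it through.** The plan gives no figure to reproduce here. The check compares windows, counts draws and traces one case through the outputs.

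**1. Windows, in Study Drug End Days (last dose = Day 0)**

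- On-treatment laboratory data end at Day 2 (SAP 6.2, Table 1 note).
- TEAEs run to Day 30 (SAP 11.2.1).
- The PT Week 4 row of SAP Table 3 reads "Post-Treatment Week 4 28 3 to 56": nominal Day 28, window Days 3 to 56.
- Days inside the TEAE period but outside the hepatic period: 3 to 30, that is 30 − 2 = 28 days. Nominal Day 28 is among them.
- Length of the PT Week 4 window: 56 − 3 + 1 = 54 days. Of these, 30 − 3 + 1 = 28 lie within 30 days of last dose and 56 − 31 + 1 = 26 lie beyond.

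**2. Scheduled post-baseline chemistry draws inside the TEAE window (Protocol Appendices C and D, nominal days)**

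| Arm | Draws | Cannot open a hepatic case |
|---|---|---|
| A | Week 4, EOT (Week 8), PT Week 4 | 1 of 3 = 33% |
| B | Week 4, Week 8, EOT (Week 12), PT Week 4 | 1 of 4 = 25% |

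PT Week 12 in Arm B is nominal Day 84, outside the 30 days, so it is not counted.

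**3. Where a PT Week 4 abnormality does appear**

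- Change from baseline by visit: included, as group statistics.
- Shift tables: not included; they are limited to the Treatment Period.
- Toxicity-grade count: SAP 11.3.2 refers to post-baseline values and states no period; Protocol 8.1.6.2 likewise speaks of the maximum post-baseline grade. A value counts only if its grade is worse than at baseline.
- Grade 2 listing: any subject with an increase to grade 2 or higher in any graded laboratory test. Bilirubin above 2 x ULN is at least grade 2 (SAP Table 10: above 1.5 to 3 x ULN). An ALT-plus-bilirubin case is therefore listed through bilirubin unless baseline bilirubin was already at that grade or worse.
- ALT above 5 x ULN is grade 3, so it is counted and listed for every subject whose baseline ALT was at or below 5 x ULN.

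**4. A case that can escape (illustrative values)**

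Entry allows ALT up to 10 x ULN (exclusion criterion 7). Take ALT of 8 x ULN at baseline, 2 at Week 4, 1 at EOT and 15 at PT Week 4.

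- Hepatic criterion: 15 exceeds 5 x ULN and the nadir of 1, but Day 28 is after Day 2, so it is not counted.
- Toxicity grade: 8 and 15 are both grade 3 (above 5 to 20 x ULN), so there is no worsening and ALT is not counted.
- Grade 2 listing: the subject appears only if another graded test, such as bilirubin or AST, worsens to grade 2 or higher.
- Protocol 6.1.7.1 repeat test: this needs more than 2 x baseline = 2 x 8 = 16 x ULN; 15 does not reach it.

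The on-treatment ALT criterion applies regardless of grade change, so the same rise at EOT would have been counted.

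**5. Likely number of cases**

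Protocol 3.0 reports 4 subjects with post-nadir grade 3 ALT, or grade 2 ALT with bilirubin at least 2 x ULN, in the pooled studies without M15-462 (N = 2,265 in Protocol Table 3). That gives 100 x 4/2,265 = 0.18 expected in 100 subjects, and a chance of at least one of 1 − (1 − 4/2,265)^100 = 0.16. The period in which those four were seen is not stated, so this indicates rarity only and is not a post-treatment rate.

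**The case against.** The strongest reply is that this is a convention and not a contradiction. The SAP also confines laboratory shift tables and potentially clinically significant vital signs to the treatment period, and nothing in either document promises that hepatic tables follow the TEAE window. That stands: the point is an improvement, not the repair of an inconsistency.

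Three stronger readings are tempting, and the documents do not support them.

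- A reader might infer that these values appear in no summary or listing at all. As traced above, the toxicity-grade count and grade 2 listing carry no stated period limit, and most combination cases would be listed through bilirubin.
- A reader might count 2 of 5 draws (40%) in Arm B by including PT Week 12. That draw lies outside the 30-day window that serves as the benchmark.
- A reader might add late EOT draws, which would make it 2 of 3 in Arm A. No document gives a frequency for these, and Protocol 5.4.1 asks for premature discontinuation visits within 2 days of the final dose.

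Other coverage exists. Hepatic decompensation events are tabulated and listed to 30 days (SAP 11.2.3), Child-Pugh shifts include post-treatment visits (SAP 11.5), and a large ALT rise triggers a repeat test. None of these counts ALT from nadir or ALT with bilirubin.

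Two objections bear on the remedy and are accepted. A 30-day cut-off would leave out PT Week 4 draws on Days 31 to 56. And simply lengthening the period would interact badly with the confirmation rule, because Arm A has no scheduled chemistry after PT Week 4. The exception for a single ALT followed by loss to follow-up could then turn a lone PT Week 4 value into a confirmed abnormality.

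**Conclusion.** The concern holds in limited form. A post-nadir ALT rise or an ALT-plus-bilirubin combination first seen at PT Week 4 cannot enter any hepatic count or hepatic listing, although the draw is scheduled for every subject inside the TEAE window. In scheduled draws this is 1 of 3 in Arm A and 1 of 4 in Arm B. In subjects it is probably few or none.

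The loss is specific: the combined count, the post-nadir count, and any flag for an ALT rebound that stays within the baseline grade while no other graded test worsens.

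This assumes draws at their nominal days and a toxicity-grade table that covers post-treatment values. If that table were programmed for the treatment period only, the gap would be wider, which is why its period should be stated. The conclusion is the same whether treatment ends at the last dose or at Study Drug End Day 2. The change is worth making because it is cheap and uses data already collected.

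**What to change.** In SAP 11.3.2:

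- Keep the on-treatment count as the main row, unchanged.
- Add a separate row and listing that apply the same criteria to values after Study Drug End Day 2 through the PT Week 4 analysis window (End Days 3 to 56). Carry the nadir over from the on-treatment series, and say how an ALT and bilirubin pair split across End Day 2 is counted.
- List any later qualifying value (PT Week 12, Arm B).
- Extend the confirmation definition to two consecutive post-treatment ALT values. Show a single PT Week 4 ALT above 5 x ULN with no later ALT as unconfirmed, outside the loss-to-follow-up exception.
- State the period of the toxicity-grade table and grade 2 listing. Correct their reference to Table 11, which holds vital signs; the laboratory grades are in Table 10.

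The cost is SAP wording, a period flag, a revised confirmation derivation, one row and one listing. No new data are needed. The downside is that a few off-drug values are reported; the separate row keeps them apart from the on-treatment count.

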11.4 Analysis of Vital Signs and Weight

11.4.1 Variables and Criteria Defining Abnormality

Vital sign variables are body temperature, sitting systolic blood pressure, sitting diastolic blood pressure, sitting pulse rate, and body weight.

The criteria for potentially clinically significant (PCS) vital sign findings are presented in [Table 11](#).

Table 11. Criteria for Potentially Clinically Significant Vital Sign Values

Test/Measurement	Very Low (VL)	Very High (VH)
Systolic Blood Pressure	≤ 90 mmHg AND A decrease of ≥ 20 mmHg from baseline	≥ 180 mmHg AND An increase of ≥ 20 mmHg from baseline
Diastolic Blood Pressure	≤ 50 mmHg AND A decrease of ≥ 15 mmHg from baseline	≥ 105 mmHg AND An increase of ≥ 15 mmHg from baseline
Pulse Rate	≤ 50 bpm AND A decrease of ≥ 15 bpm from baseline	≥ 120 bpm AND An increase of ≥ 15 bpm from baseline
Weight	A decrease of ≥ 15% from baseline	An increase of ≥ 15% from baseline
Body Temperature		> 38.3°C AND An increase of ≥ 1.1°C from baseline

11.4.2 Statistical Methods

The baseline value for vital signs will be the last measurement on or before the day of the first dose of study drug. The same baseline value will be used for changes at Treatment Period visits and changes at Post-Treatment Period visits.

Changes from baseline to each post-baseline visit, including applicable post treatment visits, will be summarized. Each vital sign parameter will be summarized with the baseline mean; visit mean; and change from baseline mean, standard deviation, minimum, median, and maximum.

The number and percentage of subjects with on-treatment values meeting the specified criteria for PCS vital sign values (Table 11) will be summarized. A post-baseline value must be more extreme than the baseline value to be considered a PCS finding. A separate listing will be provided that presents all vital sign values for the subjects meeting PCS criteria during treatment.

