8.1.2.5 Additional Efficacy Endpoints

The following additional efficacy endpoints will be summarized by genotype:

- The percentage of subjects with HCV RNA < LLOQ at each post-baseline visit in the Treatment Period (using data as observed);
- The percentage of subjects who achieve SVR 4 weeks after the last actual dose of study drug (SVR₄);

The number and percentage of subjects meeting each additional efficacy endpoint will be summarized along with a two-sided 95% confidence interval using the Wilson's score interval.

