8.1.6.3 Vital Signs Data

Mean changes in temperature, systolic and diastolic blood pressure, pulse, and weight from baseline to each post-baseline visit, including Final Treatment Visit, will be summarized descriptively. The number and percentage of subjects with post-baseline

values meeting pre-defined criteria for Potentially Clinically Significant (PCS) vital signs values will be summarized.

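### The protocol counts potentially clinically significant (PCS) vital signs on all post-baseline values; the SAP counts and lists on-treatment values only, and its list of changes, as supplied, does not say so

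*SAP*

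**What the plan says.** Protocol 8.1.6.3 defines the summary in a sentence that a page break divides. It opens "The number and percentage of subjects with post-baseline" and continues "values meeting pre-defined criteria for Potentially Clinically Significant (PCS) vital signs values will be summarized". It sets no limit to the Treatment Period.

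SAP 11.4.2 instead summarizes "The number and percentage of subjects with on-treatment values meeting the specified criteria for PCS vital sign values", using the criteria in SAP Table 11. The listing follows the same limit: "A separate listing will be provided that presents all vital sign values for the subjects meeting PCS criteria during treatment".

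For the treatment windows that apply to vital signs, the note to SAP Table 1 (section 6.2) states: "For all windows, data must be on or before Study Drug End Day 2". After treatment, the row "Vital Signs and Weight" in protocol Appendix D is marked at PT Week 4, PT Week 12 and the PT discontinuation visit. SAP Table 3 assigns windows to those measurements.

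SAP 12.1, headed as the changes between the protocol and the SAP, shows one item in the text supplied, on HIV co-infection. Material directly after it was removed from the copy under review.

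**The concern.** The same safety count is defined in two ways, and the definitions do not give the same table. A blood pressure, pulse, temperature or weight value that first meets Table 11 at PT Week 4 or PT Week 12 makes the subject a case under the protocol. Under the SAP that subject is neither counted nor shown in the PCS listing.

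Safety is one of the primary objectives in both documents. PT Week 4 is the sharper case. An adverse event starting on day 28 after the last dose is treatment-emergent under SAP 11.2.1, while a PCS vital sign on the same day falls outside the table. Adverse event reporting closes the gap only in part: under protocol 6.1.1.1 a vital-sign change becomes an adverse event only if it leads to discontinuation, needs medical intervention, or is judged an adverse event by the investigator.

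**Working it through.** **Does post-baseline mean on-treatment here?** The protocol adds a qualifier when it wants treatment visits only: section 8.1.2.5 has "at each post-baseline visit in the Treatment Period". The SAP, in the section that holds the PCS rule, has "Changes from baseline to each post-baseline visit, including applicable post treatment visits, will be summarized". Both documents therefore use the term for a set that extends past the last dose, and the two PCS definitions differ in substance. The SAP does not define on-treatment separately for this table; I take it to mean the Table 1 windows, closing at Study Drug End Day 2.

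**Scheduled post-baseline vital-sign visits** (protocol Appendices C and D)

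- Arm A: Week 4 and end of treatment at Week 8, then PT Weeks 4 and 12. On treatment 2, total 4.
- Arm B: Weeks 4 and 8 and end of treatment at Week 12, then PT Weeks 4 and 12. On treatment 3, total 5.
- Planned sizes (protocol 5.1): about 80 in Arm A, at most about 20 in Arm B.

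With full attendance:

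- All post-baseline: 80 × 4 + 20 × 5 = 420.
- On treatment: 80 × 2 + 20 × 3 = 220.
- Excluded by the SAP: 420 − 220 = 200, and 200/420 = 47.6%. By arm, 2/4 = 50% in A and 2/5 = 40% in B.
- PT Week 4 alone: 80 + 20 = 100, and 100/420 = 23.8%.

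Fewer Arm B subjects move the overall share only slightly: 200/415 = 48.2% at 85/15, and 200/400 = 50% with none. The documents state no figure for this point, so there is none to reproduce.

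**From visits to subjects.** The documents give neither a per-visit PCS rate nor a within-subject correlation, so what follows is illustration. Let p be the chance of a PCS value at a visit, equal at all visits, and ρ the within-subject correlation. Under a beta-binomial model with a = p(1 − ρ)/ρ and b = (1 − p)(1 − ρ)/ρ, the chance of no event in n visits is the product over k = 0 to n − 1 of (b + k)/(a + b + k). With ρ = 0 it is (1 − p)^n. Expected subjects = 80 × P(at least one in n_A) + 20 × P(at least one in n_B), with (n_A, n_B) = (2, 3) for the SAP, (3, 4) through PT Week 4 and (4, 5) for the protocol.

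At p = 1%:

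| ρ | SAP | Through PT Week 4 | Protocol | SAP shortfall against protocol | SAP shortfall against PT Week 4 |
|---|---|---|---|---|---|
| 0 | 2.19 | 3.16 | 4.13 | 47% | 31% |
| 0.1 | 2.05 | 2.84 | 3.56 | 42% | 28% |
| 0.3 | 1.80 | 2.31 | 2.72 | 34% | 22% |
| 0.5 | 1.56 | 1.87 | 2.11 | 26% | 17% |

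With ρ = 0, changing p to 0.5% gives 1.10 against 2.08, and to 2% gives 4.34 against 8.13. The shortfall stays near 47% because independence with a constant rate nearly returns the visit share. Correlation is what moves it.

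**The case against.** An on-treatment table is a defensible choice and fits the rest of the SAP: the laboratory shift tables and hepatic criteria in 11.3.2 are also limited to treatment. Half of the excluded visits are at PT Week 12, nominally day 84, far past the 30-day period, where a PCS value says less about the drug. That much stands. It supports showing the on-treatment count; it does not explain why the count departs from the protocol without a stated reason.

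Post-treatment extremes are also not wholly invisible. The by-visit summaries in SAP 11.4.2 give minimum and maximum change as well as means, and they cover post-treatment visits, so a large individual rise or fall may appear there. This stands too. But those figures count no subjects. For blood pressure, pulse and temperature, Table 11 requires an absolute level together with a change, and the summaries do not join the two. A subject already PCS on treatment does have all values listed; the gap concerns those who first qualify later.

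A reader might infer that the SAP rule loses nearly half of the subjects with PCS findings. The documents do not support that. The 48% is a share of visits, and it carries over to subjects only if every visit has the same, independent chance of an event. Repeated vital signs in one person are likely to be correlated, and someone abnormal after treatment may already have been counted during it.

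A reader might also infer that the change was left undeclared. That cannot be settled, because material directly after SAP 12.1 is not available; the statement holds for the text supplied only.

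**Conclusion.** The inconsistency is real. The protocol's PCS count covers all post-baseline vital signs, the SAP's count and listing stop two days after the last dose, and no reason is given in the available text. At the planned arm sizes with full attendance, 48% of scheduled post-baseline vital-sign visits cannot produce an event, and 24% are PT Week 4 visits within 30 days of the last dose. The subject-level effect is unknown. In the illustration at 1% per visit and correlations of 0.1 to 0.5, it is about 0.5 to 1.5 subjects per 100 (2.11 − 1.56 = 0.55; 3.56 − 2.05 = 1.51). Both inputs are assumptions.

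The consequence is confined to one descriptive safety table and its listing. The primary efficacy endpoint is untouched and no data are lost. It still merits correction, because the table serves a primary objective and the remedy costs very little.

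**What to change.** In SAP 11.4.2, base both the PCS count and the listing on all post-baseline values, as protocol 8.1.6.3 states. Show the findings by time: on treatment (to Study Drug End Day 2), after treatment but within 30 days of the last dose, and later. State that a subject counts once in the overall total and may appear in more than one period. The on-treatment figure then stays visible beside the protocol's total.

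If the sponsor prefers to keep only the on-treatment count, list that restriction in SAP 12.1 as a departure from the protocol and justify it.

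The cost is a short change to the SAP text and one timing flag, on data already collected. The small downside is that some late off-drug values enter the total, and the PT Week 12 window in SAP Table 3 runs to day 999. The timing split keeps those apart.
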